10.1.2. Serious Adverse Event

An SAE is any AE occurring at any dose that results in any of the following outcomes:

- death
- a life-threatening event
 - This includes any AE that in the view of either the investigator or sponsor places the subject at immediate risk of death. It does not include an AE that, had it occurred in a more serious form, might have caused death.
- requires inpatient hospitalization or prolongs existing hospitalization
 - Hospitalization signifies the subject has been admitted, regardless of duration, for observation and/or treatment that would not have been appropriate in a physician's office or outpatient setting.
 - Hospitalizations for elective or pre-planned treatment of a pre-existing condition do not have to be reported as SAEs if the following criteria are met:
 - the condition is documented in the subject's medical history and has not worsened since the informed consent form was first signed; and
 - the condition and planned procedure are documented in the subject's source records at screening.
 - Emergency room/department or outpatient treatments that do not result in admission do not have to be reported as an SAE, unless another SAE criterion is met. Events assessed and treated in these circumstances should be captured as AEs in the eCRF and documented in the subject's source records.
 - Hospitalizations solely based on subject logistics (eg, subject is admitted due to limited hospital accessibility for what would otherwise be an out-subject procedure) do not have to be reported as SAEs provided that the hospitalizations are clearly defined as such in the subject's source record.
- persistent or significant incapacity or substantial disruption of the ability to conduct normal life functions
- congenital anomaly/birth defect

An important medical event that does not result in one of the above serious outcomes may be considered an SAE when, based upon appropriate medical judgment, it may jeopardize the subject and may require medical or surgical intervention to prevent one of the listed serious outcomes. Examples of such medical events include allergic bronchospasm requiring intensive treatment in an emergency room or at home, blood dyscrasias, or convulsions that do not result in inpatient hospitalization, or development of drug dependency or drug abuse.

If the following 4 elements are known, the event must be reported as described in Section 10.4.2:

- identifiable subject
- event term
- study drug
- identifiable reporter

Additionally, the investigator's assessment of an event's relationship to study drug (see Section 10.2) is essential for the sponsor to appropriately process the report and must be included.

Subjects and parents or legally-authorized representatives must be informed and understand that they should report events meeting the definition for SAE to study site personnel as soon as possible (and not wait until their next study visit).

If a non-serious event becomes serious, the change in status must be appropriately entered in the eCRF and the subject's source record, and reported to the sponsor as described in Section 10.4.2.

If the investigator becomes aware of an SAE that occurs more than 30 days after the last dose of study drug, and considers the event possibly, probably, or definitely related to study drug, the investigator should contact the Medical Monitor (see Table 1)/Clinical Operations Lead to determine how the SAE should be documented and reported.

10.2. Relationship to Study Drug

The investigator or a medically qualified sub-investigator will review each event and assess its relationship to study drug based on available information and according to the following guidelines:

- Definite: a reaction that follows a distinct temporal relationship from administration of study drug; that follows a known reaction to the agent or chemical group of the study drug; and that cannot be explained by the subject's clinical state or other factors
- Probable: a reaction that follows a reasonable temporal sequence from administration of study drug; that follows a known or expected response pattern to the suspected study drug; and that could not be reasonably explained by the known characteristics of the subject's clinical state
- Possible: a reaction that follows a reasonable temporal sequence from administration of study drug; that follows a known or expected response pattern to the suspected study drug; but that could readily have been produced by a number of other factors
- Unlikely: a reaction that does not follow a reasonable temporal sequence from administration of study drug; however, causality from the study drug cannot be ruled out
- Unrelated: a reaction for which sufficient data exist to indicate that the etiology is unrelated to study drug

For the purpose of expedited SAE regulatory reporting obligations (ie, to regulatory authorities and Institutional Review Boards [IRBs]/Independent Ethics Committees [IECs]), events assessed by the investigator as definitely, probably, or possibly related to study drug will be considered "related" to study drug (ie, associated with the use of study drug). Events assessed as unlikely or unrelated will be considered "not related" to study drug (ie, not associated with the use of study drug).

10.3. Severity Assessment

The investigator or a qualified sub-investigator will review each event and use the following definitions for rating intensity:

- Mild: awareness of sign, symptom or event, but the AE is easily tolerated and does not interfere with daily activity
- Moderate: discomfort enough to cause interference with usual activity and may warrant intervention, but the subject is still able to function
- Severe: incapacitating with inability to do usual activities or significantly affects clinical status, and requires medical intervention

It is important to distinguish the difference between events that meet the definition of serious and events that are deemed as severe in intensity. Adverse events assessed as severe in intensity are not SAEs unless at least 1 of the definitions in Section 10.1.2 is met. Adverse events of any intensity must be reported as SAEs if at least 1 definition in Section 10.1.2 is met.

10.4. Reporting Events

10.4.1. Reporting Adverse Events

Information regarding AEs is to be obtained by questioning or examining the subject and/or parents or legally-authorized representatives.

As noted in Section 10.1.1, AEs will be recorded in the eCRF and subject source record beginning from the time written consent (assent) is provided through the follow-up visit (at least 30 days after the last dose of study drug). Required information will be detailed in the eCRF Completion Guidelines.

10.4.2. Reporting Serious Adverse Events

Serious adverse events must be documented and reported to the sponsor immediately, but no later than within 24 hours of any knowledge by study site personnel of events. Serious adverse event reports must be faxed to the designated safety fax number (Table 1) to ensure appropriate dissemination and processing of the information. An alternate email address is provided as a backup, if the fax transmission is unsuccessful.

Serious adverse event forms, which will be provided by the sponsor, should be as complete as possible, with all information known at the time included. All relevant supporting documentation (eg, admission and progress notes, results of diagnostic evaluations/procedures/examinations, etc) available at the time of reporting, should be included in the fax (or email, if necessary) along with the SAE report form. All supporting documents must be thoroughly reviewed and

de-identified in accordance with local data privacy regulations prior to sending to the sponsor. The subject's study number must be included on each page included in the faxed report or in the subject line of the email. Reporting timelines (as described above) must not be delayed while obtaining or preparing supporting information.

If more than 1 SAE is identified in 1 subject simultaneously, separate SAE reports should be generated for each event.

Information not available at the time of the initial report (eg, event end date and outcome, supporting documents (eg, discharge summary, etc) must be reported to the sponsor within **24 hours of any knowledge/receipt by study site personnel of the information**. Information must be faxed (or emailed, if necessary) to the designated safety fax number (or email address) (Table 1) to ensure appropriate dissemination and processing. All supporting documents must be thoroughly reviewed and de-identified in accordance with local data privacy regulations prior to sending to the sponsor. The subject's study number must be included on each page included in the fax or in the subject line of the email.

Medical history, concomitant medication, and AE information obtained through SAE reporting must also be consistently recorded in the eCRF.

10.4.3. Additional Reporting Requirements for Suspected Unexpected Serious Adverse Reaction

The sponsor is responsible for processing suspected unexpected serious adverse reactions (SUSARs). SUSARs are also referred to as alert reports, expedited safety reports, and investigational new drug application (IND) safety reports.

A SUSAR is defined as any SAE that is determined to be associated with the use of study drug and is unexpected (not currently listed in the safety reference information or is not listed at the specificity or severity that been observed). The sponsor will notify all investigators currently conducting migalastat clinical studies of all SUSARs in accordance with applicable regulations. SUSARs will be reported to the relevant regulatory authorities and IRBs/IECs according to the rules in effect in each country where study sites are located:

- If the SUSAR is fatal or life-threatening, regulatory authorities and ethics committees will be notified within 7 calendar days after the sponsor learns of the event.
- If the SUSAR is not fatal or life-threatening, regulatory authorities and ethics committees will be notified within 15 calendar days after the sponsor learns of the event.

These notifications will need to be filed in each site's Study File Notebook and submitted to each site's IRB/IEC in accordance with policy.

Safety updates will be provided periodically to the regulatory authorities and IRBs/IECs responsible for the study according to the rules in effect in each country where study sites are located. These updates will include information on SUSARs and other relevant safety findings.

10.5. Other Reporting Situations

10.5.1. Pregnancy

Pregnancy information for female subjects and female partners of male subjects participating in the study is collected by the sponsor. Pregnancy, in and of itself, is not regarded as an AE (unless there is a suspicion that study drug may have interfered with the effectiveness of a contraceptive medication).

If a female subject becomes pregnant during the course of the study, or if the female partner of a male subject becomes pregnant during the subject's participation in the study, the sponsor must be informed within 5 working days of any knowledge of the pregnancy by study site personnel. If an SAE occurs in conjunction with the pregnancy, the SAE must be reported as described in Section 10.4.2. The sponsor will provide pregnancy report forms (initial and follow-up) and instructions to study site personnel regarding collection of pregnancy and outcome information (subject to receipt of data privacy release approvals where required under local privacy laws). Pregnancy report forms must be faxed (or emailed, if necessary) to the designated safety fax number (or email) (Table 1) to ensure appropriate dissemination and processing of the information.

10.5.2. Medication Errors, Including Overdose and Under Dose

Medication error refers to any unintended error in the dispensing or administration of a study drug.

If a subject experiences an overdose (defined as $\geq 20\%$ higher than the assigned dose of study drug for that period in the protocol) or an under dose (defined as $\geq 20\%$ lower than the assigned dose of study drug for that period in the protocol) during the course of the study (whether symptomatic or not), the Amicus' medical monitor must be notified within 5 working days of the investigator or study staff first becoming aware of the overdose.

Medication errors, including overdose and under dose, should be captured in subjects' source records and recorded in the eCRFs. Any AE or SAE that occurs as a result of a medication error should be reported according to AE/SAE reporting requirements (see Section 10.4).

10.5.3. Reporting of Possible Study Drug Product Quality Defects

Any defect or possible defect associated with study drug must be reported to the sponsor ([contact]) within 1 working day of any study site personnel knowledge of the possible defect. The study drug and packaging components in question, if available, must be segregated and stored in a secure area at the site under the specified storage conditions (see Section 12.4) until it is determined whether or not the study drug and/or packaging is required for investigation of the possible defect. If the possible defect is associated with an SAE, the SAE must be reported as described in Section 10.4.2. The SAE report must include the possible study drug defect complaint.

11. DATA ANALYSIS AND STATISTICAL CONSIDERATIONS

Details of the data handling rules and statistical calculations will be provided in the statistical analysis plan.

11.1. Endpoints

11.1.1. Safety Endpoints

Safety endpoints are as follows:

- incidence of TEAEs, SAEs, and AEs leading to discontinuation of study drug
- changes in clinical laboratory test results from baseline over time
- changes in vital signs from baseline over time
- changes in physical examination findings from baseline over time
- change in body weight and height from baseline over time
- changes in ECG results from baseline over time
- changes in echocardiogram parameters from baseline to Month 12/ET
- change in Tanner stage from baseline to Month 12/ET
- use of concomitant medications

11.1.2. Pharmacokinetic Endpoints

Pharmacokinetic endpoints are as follows:

- population PK model that describes the relationship between weight and age and migalastat pharmacokinetics in pediatric subjects (with primary PK parameter outputs listed in the following text)
- PK parameters based on simulated plasma-concentration data for migalastat after multiple-dose administration at steady-state concentration
 - C_{max}: maximum observed plasma concentration
 - C_{min}: minimum observed plasma concentration
 - t_{max}: time to reach C_{max}
 - AUC₀₋₇: area under the plasma concentration-time curve from time 0 over the dosing interval (ie, 48 hours)
 - t_{1/2}: terminal elimination half-life
 - CL_{ss}/F: apparent oral clearance at steady-state concentration
 - V_{ss}/F: apparent oral volume of distribution at steady-state concentration

11.1.3. Pharmacodynamic Endpoints

The pharmacodynamic endpoint is the change in plasma levels of lyso-Gb₃ from baseline to Months 3, 6, and 12/ET.

11.1.4. Efficacy Endpoints

Efficacy endpoints are as follows:

- change in eGFR from baseline to Months 3, 6, and 12/ET
- change in urine protein and albumin levels from baseline to Months 3, 6, and 12/ET
- change in LVMi and other echocardiogram parameters from baseline to Month 12/ET
- change in gastrointestinal signs and symptoms and pain from baseline to Month 12/ET, as measured by e-diary responses (FABPRO-GI and Pain Questionnaire for Clinical Trials [24-hour version])
- mean PGI-C values at Months 3, 6, and 12/ET
- change in FPHPQ scores from baseline to Month 12/ET
- change in PedsQL scores from baseline to Month 12/ET

11.2. Sample Size Considerations

A sample size of at least 7 to 10 subjects per age/weight group is required for statistical comparison with adult exposure based on 2 methods described by Wang, Jadhav et al. 2012.

First, assuming the final CL/F estimates and inter-individual variability of 28.5% (Migalastat Abbreviated Report of the Simulations of Migalastat in Pediatric Patients with Fabry Disease, 16 October 2016), 7 subjects is adequate to achieve at least 80% power for a study design with rich PK sampling intended for non-compartmental analysis.

Second, according to the sample size calculation for a study with sparse/rich PK sampling intended for population PK analysis, $(e^{-t(0.975,df) \times SE_{LCL}}, e^{t(0.975,df) \times SE_{LCL}})$ should be within the pre-defined criteria of (0.6, 1.4), where SE_{LCL} is the standard error for log-transformed pediatric clearance that relates to weight, and t (0.975, df) is the 97.5% upper quantile values from t distribution corresponding to the sample size. Mathematically, SE_{LCL} was approximately equal to the relative standard error of untransformed clearance, 0.16. Therefore, a sample size of approximately 10 subjects is adequate to achieve the pre-defined boundary of (0.6, 1.4).

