8. SELECTION AND WITHDRAWAL OF SUBJECTS

8.1. Number of Subjects

Approximately 20 subjects are planned globally for enrollment in this study. An attempt will be made to enroll subjects of each sex. At least 7 to 10 of these subjects will be aged 12 to < 16 years for a subgroup analysis to be conducted at the end of Stage 1.

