11.3.2.1. Interim Analysis

The interim PK endpoint is a graphical presentation of plasma-concentration time data (observed versus predicted).

Interim analysis of the plasma concentration-time data collected during Stage 1 will be conducted when these results are available. There will be 2 interim PK analyses. One analysis will be performed using the entire Stage 1 PK population of adolescents aged 12 to < 18 years. A second analysis will include a subpopulation of at least 7 to 10 subjects age 12 to < 16 years.

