11.3.2.3. Pharmacokinetic Analyses

For the population PK analysis, predicted median (2.5^{th} and 97.5^{th} percentile) concentration-time data based on a previously established population PK model will be visually compared with observed concentration-time data for all patients and for the subgroup aged 12 to < 16 years at the end of Stage 1.

The PK analyses for the current study will be performed according to the following steps:

- Step 1: After combining previous concentration-time data from adults with pediatric data from the current study, the population PK model established previously (Migalastat Amended Population Pharmacokinetic Analysis of Migalastat, Amendment 02; Migalastat Abbreviated Report of the Simulations of Migalastat in Pediatric Patients with Fabry Disease, 20 October 2016) will be updated. Most importantly, the allometric scaling functions for CL/F and volume parameters (ie, V2/F, V3/F) will be re-evaluated and corrected, if necessary. Other covariates that are predictive of drug disposition (eg, age, weight, body surface area) may be evaluated.
- Step 2: Using the updated population PK model, clinical trial simulations will be conducted assuming administration of migalastat to steady-state concentration for each pediatric subject and for adults (with equivalent renal function) receiving migalastat HCl 150 mg every other day. The simulations will use population PK parameter uncertainty from a nonparametric bootstrap, inter-individual variability, and residual variability. At least 1000 clinical trials will be simulated assuming at least 24 subjects per age group.
- Step 3: Pharmacokinetic endpoints (ie, C_{max}, C_{min}, and AUC_{0-τ}) for migalastat will be calculated from simulated concentration-time data in pediatric groups and in adults. The AUC_{0-τ} and C_{max} in 12 to < 18 year olds will be compared to the values in adults with equivalent renal function using an analysis of variance (ANOVA). The 90% confidence intervals (CIs) for the ratio of the geometric least squares means of C_{max} and AUC_{0-τ} will be constructed for comparison of the pediatric group with adult group. These 90% CIs will be obtained by exponentiation of the 90% CIs for the difference between the least squares means based on an In-transformed scale.

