- Step 4: Exposures in the pediatric group and adults will be considered equivalent when 90% CIs of the ratio of the geometric least squares means of $AUC_{0-\tau}$ are within the range of 0.8 to 1.25 (ie, 80% to 125%). Intervals obtained from Step 3 will be evaluated according to these a priori criteria. The ratios and CIs will also be determined for C_{max} .
- Step 5: If the bioequivalence criteria cannot be met in Step 4 using the dosing regimen listed in Section 7.2.1, adjusted dosing regimens will be proposed to achieve bioequivalence considering dose proportionality, if necessary, and used for future pediatric clinical trial simulations.
- Step 6: The proposed dose for pediatric subjects (12 to < 18 years and 12 to < 16 years) will then be considered the dosage regimen producing an AUC_{0- τ} meeting the 80% to 125% rule and a C_{max} that either meets this rule or, if not possible, is as close as possible balancing the available dosage strengths with safety.

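### With SE 0.16 the printed precision formula gives (0.70, 1.44) at 10 subjects, so the claim that about 10 meets (0.6, 1.4) does not follow from the stated inputs

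*Protocol*

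**What the plan says.** Protocol 11.2 justifies 7 to 10 subjects per age/weight group by two methods. The first assumes rich sampling with non-compartmental analysis and 28.5% inter-individual variability, and arrives at 7. The second is for population PK analysis. It requires exp(-t(0.975, df) × SE) and exp(+t(0.975, df) × SE) both to fall within (0.6, 1.4). The SE in that formula "is the standard error for log-transformed pediatric clearance that relates to weight", and its value "was approximately equal to the relative standard error of untransformed clearance, 0.16". The multiplier t "is the 97.5% upper quantile values from t distribution corresponding to the sample size". The section then concludes: "Therefore, a sample size of approximately 10 subjects is adequate to achieve the pre-defined boundary of (0.6, 1.4"). The synopsis and SAP 4.3 give the same argument with the same figures.

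Protocol 8.1 carries the range into recruitment: "At least 7 to 10 of these subjects will be aged 12 to < 16 years". Total planned enrollment is about 20.

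**The concern.** The text gives a formula, an SE and a criterion, then draws a conclusion with the word 'therefore'. A reader who puts the numbers in does not reach that conclusion. The n and df to which 0.16 applies are missing, as is the resulting interval, so the reader cannot tell where the discrepancy comes from.

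The study takes four sparse samples per subject in Stage 1. The second method is thus the only calculation given for the design actually used, and it supplies the upper figure in the minimum of 7 to 10. That minimum is stated both per age/weight group and for the 12 to < 16 subgroup. As written, the reader is told that a precision target is met when the printed inputs miss it.

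**Working it through.** **Inputs, all from Protocol 11.2.** SE of log clearance 0.16; 0.975 quantile of t; criterion (0.6, 1.4); sample size about 10. No df is printed. I assume df = n - 1 and vary it.

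**The plan's own figure.** At n = 10, df = 9 and t = 2.262:

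- t × SE = 2.262 × 0.16 = 0.362
- lower limit = exp(-0.362) = 0.696, above 0.6, so it passes
- upper limit = exp(0.362) = 1.436, above 1.4, so it fails

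The stated conclusion is not reproduced.

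**Is it sensitive to df or rounding?**

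| SE | df | Upper limit |
|---|---|---|
| 0.16 | 8 | 1.446 |
| 0.16 | 9 | 1.436 |
| 0.16 | 10 | 1.428 |
| 0.155 (lowest value that rounds to 0.16) | 9 | 1.420 |
| 0.159 = sqrt(ln(1 + 0.16²)) | 9 | 1.433 |

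All fail.

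**What SE would pass at 10?** The upper limit binds. SE must be at most ln(1.4)/t = 0.3365/2.262 = 0.1487. Rounded to three decimals this has to be 0.148, because 0.149 gives 1.4008.

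**How many subjects would pass?** This depends on what 0.16 refers to.

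- Suppose 0.16 is the SE at n = 10, SE scales as 1/sqrt(n) and df = n - 1 (all assumptions). At n = 11, SE = 0.16 × sqrt(10/11) = 0.1526, t = 2.228 and the upper limit is 1.405. At n = 12, SE = 0.1461, t = 2.201 and the upper limit is 1.379. The smallest passing n is 12.
- If SE is simply held at 0.16, t must be at most 0.3365/0.16 = 2.103. That is first met at df 18 (upper limit 1.3995). Holding SE fixed while n grows is not a realistic sample-size calculation.

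**When would 10 pass?**

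- If 0.16 is the SE at 8 subjects, the same scaling gives 0.16 × sqrt(8/10) = 0.1431 at n = 10 and (0.723, 1.382), which passes. If it is the SE at 9, the upper limit is 1.410, which fails. So 10 passes if 0.16 belongs to 8 or fewer subjects.
- With an untransformed interval, 1 ± 2.262 × 0.16 = (0.638, 1.362), which passes but is not the printed formula.
- With the normal quantile 1.96 in place of t, the interval is (0.731, 1.368), which also passes and is also not the printed formula.

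The first method's variability does not reveal the source of 0.16 either: 0.285/sqrt(10) = 0.090, not 0.16.

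**The case against.** The strongest reply is that this is a gap in reporting rather than a proven miscalculation. The source calculation is not in these documents. If 0.16 was obtained at about 8 subjects or fewer, the stated conclusion could be right. That stands, and it limits the finding to what the printed inputs support.

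A second reply is that the miss is small and the text says 'approximately' 10. This also has force: under 1/sqrt(n) scaling the shortfall is 10 against 12. It does not rescue the sentence, which says the boundary is achieved.

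A third is that nothing downstream depends on the criterion. That is largely true. The range (0.6, 1.4) appears only in the sample-size text. Protocol 11.3.2.1 makes the interim comparison graphical. Protocol 11.3.2.3 judges exposure equivalence by a 90% confidence interval against 0.8 to 1.25, from simulations with at least 24 subjects per age group.

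Three stronger readings are tempting, and the documents do not support them:

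- That 10 subjects is inadequate. This needs the n behind 0.16, which is not given.
- That 19 subjects are needed (df 18 plus 1). This comes only from freezing SE at 0.16.
- That 7 subjects also breaks the rule. The formula at the same SE does give (0.676, 1.479) at df 6, but the 7 comes from the rich-sampling method and is never claimed to meet (0.6, 1.4).

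**Conclusion.** The conclusion is wrong as written, with minor effect. With the printed formula and SE 0.16, the interval at 10 subjects is (0.70, 1.44), and the upper limit exceeds 1.4 by 0.036. This assumes df = n - 1, but df of 8 or 10 and rounding of 0.16 lead to the same result. Whether 10 is in fact enough cannot be settled from these documents. It depends on the n and df behind 0.16 and on whether the printed formula is the one that was used. No analysis or decision rule changes. What is affected is the stated precision for a group of about 10, including the 12 to < 16 subgroup, for which 7 to 10 is a minimum and not a planned size.

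**What to change.** In the synopsis, Protocol 11.2 and SAP 4.3:

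1. State the n and df to which the SE of 0.16 refers.
2. Replace the concluding sentence with the interval that the stated formula gives at n = 10.
   - If 0.16 is the SE at 10, say that the interval is (0.70, 1.44) and does not meet (0.6, 1.4).
   - If 0.16 belongs to another n, give the SE at n = 10. It must be no more than 0.1487 (0.148 rounded down) at df 9 for the conclusion to hold. Take it from the model and not from assumed 1/sqrt(n) scaling, because the population analysis is fitted "After combining previous concentration-time data from adults with pediatric data from the current study".
   - If a different interval was used, correct the printed formula to match.

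An interval for n = 7 may be added as context, labelled as outside the second method's claim.

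The cost is wording in three places and one lookup in the source calculation. The downside is that the stated precision may become slightly less favourable.
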